Data Analysis for Drug Repurposing for Effective Alzheimer's Medicines – Propranolol/Carvedilol vs Atenolol/Bisoprolol/Sotalol

NCT05794997

July 7, 2023

1. Comparison Details

a. Intended aim(s)

To evaluate the comparative risk of dementia onset between patients treated with Propranolol or Carvedilol versus Atenolol, Bisoprolol, Sotalol for hypertension.

b. Primary endpoint

Incident dementia (i.e., Alzheimer's disease, vascular dementia, senile, presenile, or unspecified dementia, or dementia in other diseases classified elsewhere).

2. Person responsible for implementation of replication in Action

[name]

3. Data Source(s)

Medicare, 2008-2019

4. Study Design Diagrams

[figure not shown]
[figure not shown]

Figure- Alternate analysis approaches

■■■ Included person-time
■■■ Excluded person-time

5. Cohort Identification

a. Cohort Summary

This study will employ a new user, active comparator, observational cohort study design comparing Propranolol or Carvedilol to hydrochlorothiazide. The patients will be required to have continuous enrollment during the baseline period of 365 days before initiation of Propranolol or Carvedilol or Atenolol, Bisoprolol or Sotalol (index date). Follow-up for the outcome (dementia) differs between analyses. Follow-up begins the day after drug initiation (analysis 1, 3, 4); 180 days after drug initiation (analysis 2).

b. Key details regarding cohort creation

Index date:

- Day of initiation of new Propranolol or Carvedilol or Atenolol, Bisoprolol or Sotalol use

Inclusion criteria for analyses 1, 3, 4:

- Aged \geq 65 years on the index date
- 365 days enrollment in Medicare Parts A, B, and D with no HMO coverage
- No use of Propranolol, Carvedilol, Atenolol, Bisoprolol, Sotalol any time prior to index date (all available lookback approach with a minimum of 365 days)
- No use of Propranolol, Carvedilol and Atenolol, Bisoprolol, Sotalol concomitantly on index date
- No diagnosis of dementia any time prior to and including index date
- At least 1 inpatient claim or 2 outpatient claims with hypertension diagnosis recorded in 365 days prior to index date

Inclusion criteria for analysis 2:

- Aged \geq 65 years on the index date
- 365 days enrollment in Medicare Parts A, B, and D with no HMO coverage
- No use of Propranolol, Carvedilol, Atenolol, Bisoprolol, Sotalol any time prior to index date (all available lookback approach with a minimum of 365 days)
- No use of Propranolol, Carvedilol and Atenolol, Bisoprolol, Sotalol concomitantly on index date
- No diagnosis of dementia any time prior to and including index date
- At least 1 inpatient claim or 2 outpatient claims with hypertension diagnosis recorded in 365 days prior to index

DREAM study protocol - Comparison 13 Propranolol or Carvedilol vs Atenolol, Bisoprolol, Sotalol

date

- 180-day continuous use of Propranolol or Carvedilol or Atenolol, Bisoprolol, Sotalol starting on the index date

c. Flowchart of the study cohort assembly

	Less Excluded Patients	Remaining Patients
All patients		27,099,355
Did not meet cohort entry criteria	-20,951,408	6,147,947
Excluded due to insufficient enrollment	-2,442,601	3,705,346
Excluded due to prior use of referent	-1,096,162	2,609,184
Excluded due to prior use of exposure	-1,644,383	964,801
Excluded because patient qualified in >1 exposure category	-88	964,713
Excluded based on Dementia Exclusion	-55,850	908,863
Excluded based on Nursing home admission	-46,478	862,385
Excluded based on Propranolol/Carvedilol OR Atenolol / Bisoprolol / Sotalol Copy	-27,923	834,462
Excluded based on Propranolol / Carvedilol AND Atenolol / Bisoprolol / Sotalol concomitantly on index date Copy	0	834,462
Excluded based on Hypertension: 1 inpatient or 2 outpatient claims within 365 days	-15,211	819,251
Excluded based on Age < 65 years	-1,914	817,337
Final cohort		817,337

6. Variables

a. Exposure-related variables:

Study drug:

The study exposure of interest is initiation of Propranolol or Carvedilol

Comparator:

Initiation of Atenolol, Bisoprolol or Sotalol

b. Covariates:

Demographics	
Age	Region
Gender	Calendar year of index date
Race	Low income subsidy
Dementia risk factors	
Diabetes	Anxiety
Obesity	Bipolar disorder
Coronary artery disease	Schizophrenia
Depression	
Markers for healthy behavior, frailty, healthcare use	
Smoking	Number of hospitalizations
Mammography	Number of physician office visits
Colonoscopy	Number of serum creatinine tests ordered
Fecal occult blood test	Composite frailty score
Influenza vaccination	Number of C-reactive protein tests ordered
Pneumococcal vaccination	Osteoporosis
Herpes zoster vaccination	Fractures

Bone mineral density test	Falls
Number of distinct generic agents	Use of supplemental oxygen
Number of emergency room visits	Combined comorbidity score
Number of outpatient visits	Number of Cardiologist visits

Comedication use	
Lithium	Nitrates
Anti-epileptic mood stabilizers	Lipid lowering drugs
Anti-epileptics (other than mood stabilizers)	Non-insulin diabetes medications
Atypical antipsychotics	Insulin
Benzodiazepines	Antidepressants
Serotonin-norepinephrine reuptake Inhibitors	Typical antipsychotics
Selective serotonin reuptake inhibitors	Anticoagulants
Tricyclic antidepressants (TCAs)	Antiplatelet agents

Comorbid conditions	
Atrial fibrillation	Chronic liver disease
Coronary artery disease	Asthma
Heart failure	Ischemic heart disease
Stroke or transient ischemic attack	Chronic obstructive pulmonary disease
Peripheral vascular disease	Malignancy
Hyperlipidemia	Drug or alcohol abuse or dependence
Renal dysfunction	Venous thromboembolism

ICD-9, ICD-10, HCPCS, and NDC codes used to define the covariates listed above are available in Appendix A.

c. Outcome variables and study follow-up:

- **Primary outcome:** incident dementia, i.e., Alzheimer's disease, vascular dementia, senile, presenile, or unspecified dementia, or dementia in other diseases classified elsewhere. Outcome will be defined by 1 inpatient claim or 2 outpatient claims in analysis 1, 2, 3. In analysis 4, the outcome will be defined by 1 inpatient or 1 outpatient claims and 1 prescription claim for a symptomatic treatment [donepezil, galantamine, rivastigmine, and memantine] within 6 months of each other with outcome date assigned to second event in the sequence.

- Secondary outcomes: Individual component:
Alzheimer's disease

Condition	ICD-9 and ICD-10 codes
Alzheimer's disease	331.0*, F00*, G30*
Vascular dementia	290.4*, F01*
Senile, presenile, or unspecified dementia	290.0*, 290.1*. 290.3*, 797*, F03*
Dementia in other diseases classified elsewhere	331.1*, 331.2*, 331.7*, 294.1*, F02*

For analysis 1,3, and 4 the follow-up will start the day after initiation of Propranolol or Carvedilol and Atenolol, Bisoprolol or Sotalol and will continue until the earliest date of the following events:

- The first occurrence of the outcome of interest
- The date of end of continuous registration in the database,
- End of the study period,
- Measured death event occurs,
- The date of drug discontinuation, defined as the date of the last continuous treatment episode of the index drug (Propranolol or Carvedilol and hydrochlorothiazide) plus a defined grace period (i.e., 90 days after the end of the last prescription's days' supply in main analyses).

For analysis 2, the follow-up will start 180 days after initiation of Propranolol or Carvedilol and Atenolol, Bisoprolol or Sotalol and will continue until the earliest date of the following events:

- The first occurrence of the outcome of interest, unless otherwise specified for selected outcomes,
- The date of end of continuous registration in the database,
- End of the study period,
- Measured death event occurs,
- Maximum allowed follow-up time (1095 days) reached

7. Propensity score analysis

We will use a propensity-score (PS)¹-based approach to account for measured confounding in this study. The PS will be calculated as the predicted probability of initiating the exposure of interest (i.e., the repurposing candidate) versus the reference drug conditional on baseline covariates using multivariable logistic regression constructed separately in each data source. On average, patients with similar PSs have similar distribution of potential confounders used to estimate the PS. Therefore, analyses conditioned on the PS provide effect estimates that are free from measured confounding. For all our analyses, initiators of each exposure of interest will be matched with initiators of the reference exposure based on their PS within each data source.² Pair matching will be conducted using a nearest-neighbor algorithm, which seeks to minimize the distance between propensity scores in each pair of treated and reference patients,³ and a caliper of 0.025 on the natural scale of the PS will be used to ensure similarity between the matched patients.⁴

We report multiple diagnostics for PS analysis in this protocol. First, the PS distributional overlap is provided between two groups before and after matching to ensure comparability of these groups.⁵ Next, balance in each individual covariate between two treatment groups is reported using standardized differences.⁶

8. Table for covariate balance

Variable	Crude			PS-Matched		
	Propranolol and Carvedilol (N = 583,870)	Atenolol, Bisoprolol, Sotalol (N = 233,467)	St. Diff	Propranolol and Carvedilol (N = 222,015)	Atenolol, Bisoprolol, Sotalol (N = 222,015)	St. Diff
Demographics						
Age, mean (SD)	75.02 (7.00)	74.75 (6.77)	0.04	74.77 (6.82)	74.75 (6.78)	0.00
Gender, n (%)						
Male	281,232 (48.2%)	97,628 (41.8%)	0.13	93,749 (42.2%)	94,142 (42.4%)	0.00
Female	302,638 (51.8%)	135,839 (58.2%)	-0.13	128,266 (57.8%)	127,873 (57.6%)	0.00
Race, n (%)						
White	451,438 (77.3%)	186,360 (79.8%)	-0.06	177,198 (79.8%)	176,941 (79.7%)	0.00
Black	79,181 (13.6%)	23,050 (9.9%)	0.12	22,448 (10.1%)	22,557 (10.2%)	0.00
Hispanic	18,869 (3.2%)	7,616 (3.3%)	-0.01	7,289 (3.3%)	7,209 (3.2%)	0.01
Asian	16,471 (2.8%)	8,738 (3.7%)	-0.05	7,954 (3.6%)	8,042 (3.6%)	0.00
North American Native	3,845 (0.7%)	1,494 (0.6%)	0.01	1,347 (0.6%)	1,426 (0.6%)	0.00
Other	10,192 (1.7%)	4,575 (2.0%)	-0.02	4,242 (1.9%)	4,273 (1.9%)	0.00
Unknown	3,874 (0.7%)	1,634 (0.7%)	0.00	1,537 (0.7%)	1,567 (0.7%)	0.00
Region, n (%)						
Northeast; n (%)	79,800 (13.7%)	41,038 (17.6%)	-0.11	37,554 (16.9%)	37,805 (17.0%)	0.00
South; n (%)	275,558 (47.2%)	102,251 (43.8%)	0.07	99,500 (44.8%)	98,821 (44.5%)	0.01
Midwest; n (%)	127,682 (21.9%)	49,611 (21.2%)	0.02	47,379 (21.3%)	47,515 (21.4%)	0.00
West; n (%)	99,172 (17.0%)	39,516 (16.9%)	0.00	37,582 (16.9%)	37,874 (17.1%)	-0.01
Other; n (%)	1,658 (0.3%)	1,051 (0.5%)	-0.03			
Calendar year of index date, n (%)						
2008	41,242 (7.1%)	22,822 (9.8%)	-0.10	21,021 (9.5%)	20,784 (9.4%)	0.00

DREAM study protocol - Comparison 13 Propranolol or Carvedilol vs Atenolol, Bisoprolol, Sotalol

2009	41,633 (7.1%)	23,317 (10.0%)	-0.10	21,612 (9.7%)	21,325 (9.6%)	0.00
2010	33,970 (5.8%)	14,179 (6.1%)	-0.01	13,633 (6.1%)	13,538 (6.1%)	0.00
2011	31,276 (5.4%)	12,573 (5.4%)	0.00	12,160 (5.5%)	12,081 (5.4%)	0.00
2012	29,262 (5.0%)	11,653 (5.0%)	0.00	11,275 (5.1%)	11,283 (5.1%)	0.00
2013	79,415 (13.6%)	36,290 (15.5%)	-0.05	34,117 (15.4%)	34,212 (15.4%)	0.00
2014	77,490 (13.3%)	32,016 (13.7%)	-0.01	30,163 (13.6%)	30,408 (13.7%)	0.00
2015	71,638 (12.3%)	27,434 (11.8%)	0.02	26,098 (11.8%)	26,324 (11.9%)	0.00
2016	48,353 (8.3%)	15,916 (6.8%)	0.06	15,423 (6.9%)	15,491 (7.0%)	0.00
2017	42,820 (7.3%)	12,385 (5.3%)	0.08	12,062 (5.4%)	12,146 (5.5%)	0.00
2018	44,058 (7.5%)	12,714 (5.4%)	0.09	12,447 (5.6%)	12,493 (5.6%)	0.00
2019	42,713 (7.3%)	12,168 (5.2%)	0.09	12,004 (5.4%)	11,930 (5.4%)	0.00
Low income subsidy, n (%)	163,393 (28.0%)	60,269 (25.8%)	0.05	58,330 (26.3%)	58,026 (26.1%)	0.00
Dementia risk factors, n (%)						
Anxiety	88,780 (15.2%)	33,787 (14.5%)	0.02	32,757 (14.8%)	32,295 (14.5%)	0.01
Bipolar disorder	6,969 (1.2%)	2,315 (1.0%)	0.02	2,299 (1.0%)	2,263 (1.0%)	0.00
Coronary artery disease	333,862 (57.2%)	99,371 (42.6%)	0.30	96,483 (43.5%)	96,613 (43.5%)	0.00
Depression	93,473 (16.0%)	33,665 (14.4%)	0.04	32,918 (14.8%)	32,329 (14.6%)	0.01
Diabetes, n (%)	451,149 (77.3%)	176,186 (75.5%)		168,274 (75.8%)	168,200 (75.8%)	0.00
Obesity	148,289 (25.4%)	50,211 (21.5%)	0.09	48,216 (21.7%)	48,375 (21.8%)	0.00
Schizophrenia	3,054 (0.5%)	1,101 (0.5%)	0.00	1,045 (0.5%)	1,064 (0.5%)	0.00
Markers for healthy behavior, frailty, healthcare use						
Bone mineral density test, n (%)	247 (0.0%)	135 (0.1%)	-0.04	141 (0.1%)	123 (0.1%)	0.00
Colonoscopy, n (%)	64,492 (11.0%)	26,148 (11.2%)	-0.01	24,751 (11.1%)	24,752 (11.1%)	0.00
Fecal occult blood test, n (%)	43,860 (7.5%)	19,665 (8.4%)	-0.03	18,342 (8.3%)	18,285 (8.2%)	0.00
Influenza vaccination, n (%)	355,785 (60.9%)	143,137 (61.3%)	-0.01	136,240 (61.4%)	136,167 (61.3%)	0.00

DREAM study protocol - Comparison 13 Propranolol or Carvedilol vs Atenolol, Bisoprolol, Sotalol

Mammography, n (%)	87,549 (15.0%)	43,295 (18.5%)	-0.09	40,715 (18.3%)	40,590 (18.3%)	0.00
Pneumococcal vaccination, n (%)	169,570 (29.0%)	55,949 (24.0%)	0.11	54,070 (24.4%)	54,269 (24.4%)	0.00
Smoking, n (%)	177,079 (30.3%)	54,670 (23.4%)	0.16	52,411 (23.6%)	52,816 (23.8%)	0.00
Number of C-reactive protein tests ordered, mean (SD)	0.21 (0.81)	0.21 (0.81)	0.00	0.21 (0.86)	0.21 (0.80)	0.00
Number of emergency room visits, mean (SD)	1.87 (3.20)	1.50 (2.71)	0.12	1.51 (3.04)	1.51 (2.69)	0.00
Number of distinct prescriptions, mean (SD)	14.66 (6.45)	13.23 (6.36)	0.22	13.44 (6.02)	13.34 (6.39)	0.02
Number of hospitalizations, mean (SD)	0.90 (1.23)	0.61 (1.02)	0.26	0.61 (1.00)	0.62 (1.03)	-0.01
Number of outpatient visits, mean (SD)	14.81 (17.01)	15.01 (18.07)	-0.01	15.04 (19.64)	14.87 (17.37)	0.01
Number of physician office visits, mean (SD)	5.43 (10.24)	5.76 (11.48)	-0.03	5.77 (12.39)	5.68 (10.95)	0.01
Number of Cardiologist visits, mean(SD)	4.28 (5.14)	3.70 (5.00)	0.11	3.66 (4.93)	3.67 (4.98)	0.00
Number of serum creatinine tests ordered, mean (SD)	4.37 (3.94)	3.85 (3.32)	0.14	3.90 (3.48)	3.88 (3.34)	0.01
Composite frailty score, mean (SD)	0.22 (0.06)	0.20 (0.06)	0.33	0.20 (0.06)	0.20 (0.06)	0.00
Falls, n (%)	29,969 (5.1%)	10,173 (4.4%)	0.03	9,818 (4.4%)	9,782 (4.4%)	0.00
Fractures, n (%)	41,635 (7.1%)	15,605 (6.7%)	0.02	14,813 (6.7%)	14,855 (6.7%)	0.00
Osteoporosis, n (%)	63,351 (10.9%)	28,996 (12.4%)	-0.05	27,367 (12.3%)	27,019 (12.2%)	0.00
Use of supplemental oxygen, n (%)	21,888 (3.7%)	5,840 (2.5%)	0.07	5,735 (2.6%)	5,696 (2.6%)	0.00
Combined comorbidity score, mean (SD)	5.66 (3.07)	4.41 (2.76)	0.43	4.48 (2.71)	4.47 (2.79)	0.00
Comedication use, n (%)						

DREAM study protocol - Comparison 13 Propranolol or Carvedilol vs Atenolol, Bisoprolol, Sotalol

Antidepressants	155,811 (26.7%)	57,867 (24.8%)	0.04	56,683 (25.5%)	55,691 (25.1%)	0.01
Insulin	136,095 (23.3%)	36,934 (15.8%)	0.19	36,455 (16.4%)	36,240 (16.3%)	0.00
Lipid lowering drugs	443,656 (76.0%)	163,735 (70.1%)	0.13	157,484 (70.9%)	157,194 (70.8%)	0.00
Nitrates	128,629 (22.0%)	33,284 (14.3%)	0.20	32,638 (14.7%)	32,626 (14.7%)	0.00
Non-insulin diabetes medications	310,939 (53.3%)	122,525 (52.5%)	0.02	117,674 (53.0%)	117,427 (52.9%)	0.00
Anticoagulants	107,632 (18.4%)	55,118 (23.6%)	-0.13	49,968 (22.5%)	49,752 (22.4%)	0.00
Anti-epileptic mood stabilizers	8,005 (1.4%)	2,725 (1.2%)	0.02	2,764 (1.2%)	2,658 (1.2%)	0.00
Antiplatelet agents	146,057 (25.0%)	38,480 (16.5%)	0.21	37,748 (17.0%)	37,750 (17.0%)	0.00
Atypical antipsychotics	11,643 (2.0%)	4,105 (1.8%)	0.01	4,059 (1.8%)	3,978 (1.8%)	0.00
Benzodiazepines	74,533 (12.8%)	28,965 (12.4%)	0.01	28,241 (12.7%)	27,664 (12.5%)	0.01
Lithium	797 (0.1%)	237 (0.1%)	0.00	228 (0.1%)	233 (0.1%)	0.00
Anti-epileptics (other than mood stabilizers)	108,520 (18.6%)	35,720 (15.3%)	0.09	35,144 (15.8%)	34,621 (15.6%)	0.01
Serotonin-norepinephrine reuptake inhibitors	29,400 (5.0%)	10,743 (4.6%)	0.02	10,731 (4.8%)	10,428 (4.7%)	0.00
Selective serotonin reuptake inhibitors	93,719 (16.1%)	34,751 (14.9%)	0.03	33,965 (15.3%)	33,404 (15.0%)	0.01
Tricyclic antidepressants (TCAs)	25,906 (4.4%)	10,286 (4.4%)	0.00	10,022 (4.5%)	9,858 (4.4%)	0.00
Typical antipsychotics	2,396 (0.4%)	942 (0.4%)	0.00	924 (0.4%)	905 (0.4%)	0.00
Comorbid conditions, n (%)						
Atrial fibrillation	153,296 (26.3%)	79,342 (34.0%)	-0.17	71,905 (32.4%)	71,714 (32.3%)	0.00
Asthma	104,291 (17.9%)	35,409 (15.2%)	0.07	34,135 (15.4%)	33,885 (15.3%)	0.00
Chronic obstructive pulmonary disease	175,599 (30.1%)	58,758 (25.2%)	0.11	56,819 (25.6%)	56,347 (25.4%)	0.00
Chronic liver disease	52,786 (9.0%)	17,419 (7.5%)	0.05	16,869 (7.6%)	16,796 (7.6%)	0.00

DREAM study protocol - Comparison 13 Propranolol or Carvedilol vs Atenolol, Bisoprolol, Sotalol

Drug or alcohol abuse or dependence	77,453 (13.3%)	23,239 (10.0%)	0.10	22,489 (10.1%)	22,579 (10.2%)	0.00
Heart failure	279,855 (47.9%)	60,940 (26.1%)	0.46	60,752 (27.4%)	60,584 (27.3%)	0.00
Hyperlipidemia	510,009 (87.3%)	201,744 (86.4%)	0.03	192,105 (86.5%)	191,970 (86.5%)	0.00
Ischemic heart disease	348,401 (59.7%)	107,358 (46.0%)	0.28	104,109 (46.9%)	104,139 (46.9%)	0.00
Malignancy	156,428 (26.8%)	62,247 (26.7%)	0.00	59,313 (26.7%)	58,882 (26.5%)	0.00
Peripheral vascular disease	129,600 (22.2%)	40,710 (17.4%)	0.12	39,670 (17.9%)	39,327 (17.7%)	0.01
Renal dysfunction	236,212 (40.5%)	56,863 (24.4%)	0.35	56,068 (25.3%)	56,128 (25.3%)	0.00
Stroke or transient ischemic attack	68,173 (11.7%)	23,278 (10.0%)	0.05	22,586 (10.2%)	22,216 (10.0%)	0.01
Venous thromboembolism	37,549 (6.4%)	11,617 (5.0%)	0.06	11,391 (5.1%)	11,122 (5.0%)	0.00

9. Statistical analysis plans

Incidence rates for the outcome will be estimated for the treatment and reference groups before and after PS matching. The competing risk of death could be of concern for the current set of analyses if mortality is frequent among patients included in the cohort and if differences in the risk of mortality between treatment and reference groups are substantial. In the PS-matched sample, we will use cause-specific hazard models⁷ to provide hazard ratios averaged over the entire follow-up period as well as interval specific hazard ratios (1, 2, and 3 years) for the association between the treatment of interest and risk of ADRD after considering all-cause mortality as a competing event. Pre-specified subgroup analyses will be conducted based on age, sex, and baseline cardiovascular disease. In addition to the Medicare dataset, we will pursue a similar analysis within Clinical Practice Research Datalink (CPRD), a UK population health dataset, to validate our results.

10. References

4. Austin PC. Some Methods of Propensity-Score Matching had Superior Performance to Others: Results of an Empirical Investigation and Monte Carlo simulations. *Biometrical Journal*. 2009;51(1):171-184.

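### Sotalol is pooled into a comparator meant for hypertension, and matching on recorded atrial fibrillation may leave residual confounding by rhythm-control indication that no planned analysis examines

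*Combined protocol and SAP*

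**What the plan says.** Section 1a frames the question as "patients treated with Propranolol or Carvedilol versus Atenolol, Bisoprolol, Sotalol for hypertension". Section 6a defines the comparator as "Initiation of Atenolol, Bisoprolol or Sotalol", without distinguishing the three agents.

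In Section 5b the indication is put into practice as "At least 1 inpatient claim or 2 outpatient claims with hypertension diagnosis recorded in 365 days prior to index date". This requires the diagnosis to be on file; it does not require that the drug was prescribed for it. One list serves under "Inclusion criteria for analyses 1, 3, 4", and it excludes neither sotalol nor AF. Analysis 2 keeps sotalol by name: "180-day continuous use of Propranolol or Carvedilol or Atenolol, Bisoprolol, Sotalol starting on the index date".

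Section 6b lists AF among the comorbid conditions and anticoagulants among the comedications. It lists no antiarrhythmic drug, no cardioversion or ablation, and no arrhythmia other than AF. Section 7 applies 1:1 PS matching to every analysis. The AF row of the Section 8 table reads "Atrial fibrillation 153,296 (26.3%) 79,342 (34.0%) -0.17 71,905 (32.4%) 71,714 (32.3%) 0.00" (crude exposed, crude comparator, standardized difference, then the same for the matched groups).

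Section 9 plans subgroups by age, by sex and by cardiovascular disease at baseline, the last undefined, and a similar analysis in CPRD. It plans no result by ingredient and none without sotalol.

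**The concern.** The crude table has an unusual pattern. The propranolol/carvedilol group is sicker on heart failure (47.9% vs 26.1%), ischemic heart disease (59.7% vs 46.0%) and renal dysfunction (40.5% vs 24.4%). AF and anticoagulant use run the other way: 26.3% vs 34.0% and 18.4% vs 23.6%. A comparator with about half the heart failure but more AF is what one would expect if some of its members were started on treatment for an arrhythmia, and sotalol is the obvious candidate.

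A yes/no AF covariate does not separate a patient chosen for rhythm control from one managed by rate control. A matched pair can agree on AF and differ on that choice. If the choice goes with dementia risk, or with the chance of dementia being recorded, beyond what the other covariates capture, the hazard ratio carries part of it. Any effect of sotalol itself is also averaged into the reference group. The reader cannot judge how much this matters, because the plan never says how many comparators started sotalol.

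**Working it through.** **1. Reproduce the plan's balance figures.** Inputs are the Section 8 counts. Standardized difference = (p1 − p0) / √{[p1(1 − p1) + p0(1 − p0)]/2}.

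- AF, crude: p1 = 153,296/583,870 = 0.2626 and p0 = 79,342/233,467 = 0.3398, giving −0.169 (plan: −0.17).
- AF, matched: 71,905/222,015 = 0.3239 and 71,714/222,015 = 0.3230, giving 0.002 (plan: 0.00).
- Anticoagulants: −0.127 crude (plan: −0.13) and 0.002 matched (plan: 0.00).

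The table is sound on these rows.

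**2. What the hypertension filter does.** The Section 5c row "Excluded based on Hypertension: 1 inpatient or 2 outpatient claims within 365 days" removes 15,211 of 834,462, or 1.8% at that step. Even a filter that removed more would show only that the diagnosis is present, not why the drug was started.

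**3. What matching does to AF.** Unmatched comparators: 233,467 − 222,015 = 11,452. Of these, 79,342 − 71,714 = 7,628 have AF, or 66.6%, against 34.0% in the whole comparator. Matching therefore trims the AF-heavy end, but 71,714 comparators with AF (32.3%) remain.

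**4. How large the sotalol share could be.** The plan does not give it. Assume that every sotalol initiator has AF and that a fraction a of the other comparators has AF. Then s + (1 − s)a = p0, so s = (p0 − a)/(1 − a).

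| Sample | p0 | Assumed a | Share s |
|---|---|---|---|
| Crude | 0.3398 | 0.20 | 17.5% |
| Crude | 0.3398 | 0.2626 (exposed group's value) | 10.5%, about 24,400 patients |
| Crude | 0.3398 | 0.30 | 5.7% |
| Matched | 0.3230 | 0.2626 | 8.2%, about 18,200 patients |

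These are conditional values, not bounds.

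**5. What a residual difference would do.** Let r be the dementia rate ratio of sotalol initiators against otherwise similar comparators, after the matched covariates. Under a true null, the apparent hazard ratio is 1/(1 − s + s·r). Both s and r are assumptions.

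| s | r = 0.8 | r = 1.25 |
|---|---|---|
| 5% | 1.010 | 0.988 |
| 10% | 1.020 | 0.976 |
| 20% | 1.042 | 0.952 |

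**6. Against precision.** The plan gives no event count. With E events in two equal groups, the 95% half-width for the log hazard ratio is about 1.96 × 2/√E = 3.92/√E. A 2% shift equals that half-width at E = (3.92/0.02)² ≈ 38,400, which is 8.6% of the 444,030 matched patients. With fewer events the shift lies inside the interval.

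**The case against.** **The premise is not in the documents.** Nothing in the plan says sotalol is used for rhythm control, and the AF excess is not split by drug; it could come from atenolol or bisoprolol. This stands. The crude pattern is consistent with the concern but does not prove it.

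**Matching already handles most of the named pathways.** The matched groups agree on AF and anticoagulants, and also on heart failure (27.4% vs 27.3%), stroke/TIA (10.2% vs 10.0%), frailty score (0.20 vs 0.20), comorbidity score (4.48 vs 4.47) and cardiologist visits (3.66 vs 3.67). No standardized difference among these exceeds 0.01. This largely stands. A reader might infer that the matched contrast sets AF patients against patients without AF, or that nothing in the plan addresses the imbalance; the table contradicts both. What remains is only confounding by rhythm-control choice beyond all of these covariates.

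**Mixed indication is not peculiar to sotalol.** Heart failure is far commoner in the crude exposed group, so dropping sotalol would not leave a comparison purely of drugs prescribed for hypertension. This is correct, though heart failure is a matched covariate and rhythm-control history is not.

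**Other planned analyses may help.** The cardiovascular subgroup is undefined and does not name AF, and the CPRD analysis is described only as similar. Neither is stated to remove sotalol.

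**Conclusion.** The concern holds in a limited form. On the page, sotalol is pooled in every analysis, the indication filter is a diagnosis code, the PS has no rhythm-control covariate beyond AF yes/no, and no counts by ingredient are given. Residual confounding by rhythm-control indication is therefore possible in the matched sample, and the plan offers no way to check it.

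The size and sign are unknown. Under the assumptions shown, shifts of about 1% to 5% in either direction arise for shares of 5% to 20%. A reader might take the 10% share as an upper limit, or conclude that sotalol explains the AF excess or that the main result is invalid for hypertension. The documents support none of these: the share depends on an assumed AF prevalence among the other comparators, and the rate ratio is not given anywhere. This is a modest-priority improvement.

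**What to change.** - **Section 9:** pre-specify a sensitivity analysis of propranolol/carvedilol against atenolol/bisoprolol only, with the PS re-estimated and the groups re-matched. Report it beside the main estimate whatever it shows. It should not replace the primary conclusion if the two differ: a switch that depends on the results would need a definition of disagreement, and differences of a few percent may be hard to tell from noise.
- **Section 6b:** add baseline antiarrhythmic drug use and cardioversion or ablation to the PS for all analyses. This will not capture patients whose first rhythm-control treatment is sotalol itself, so it complements the sensitivity analysis and does not replace it.
- **Section 8:** report comparator counts by ingredient, before and after matching.
- **Section 9:** define the cardiovascular-disease subgroup and say whether it includes AF.

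The cost is one extra match, a few code lists and fewer pairs in the sensitivity analysis: about 222,015 × 0.90 ≈ 200,000 at a 10% sotalol share, or 222,015 × 0.80 ≈ 178,000 at 20%. The main analysis keeps its comparator.

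### Do the unexplained jumps in new-user counts in 2013 and 2016 undermine the new-user rule or the matched comparison?

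*Combined protocol and SAP*

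**What the plan says.** Section 3 of the combined protocol and SAP names the source in one line, "Medicare, 2008-2019". The readable text gives no first claims date and says nothing about extracts or sampling.

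Section 5b requires "365 days enrollment in Medicare Parts A, B, and D with no HMO coverage" before the index date. It judges earlier use of the study drugs by an "all available lookback approach with a minimum of 365 days", and also requires "No diagnosis of dementia any time prior to and including index date". The flowchart in section 5c has two prior-use lines, "Excluded due to prior use of referent" (1,096,162) and "Excluded due to prior use of exposure" (1,644,383).

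Section 6b lists index year as a covariate. Section 7 builds the propensity score (PS) from baseline covariates, with models "constructed separately in each data source", and matches one to one. Section 8 tabulates entrants by index year, crude and matched. Section 9 states: "Pre-specified subgroup analyses will be conducted based on age, sex, and baseline cardiovascular disease". It also plans a similar analysis in CPRD.

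**The concern.** New-user status and freedom from dementia both depend on how much history can be seen. With all-available look-back, that length varies from patient to patient. A near-tripling of entrants in one year suggests that the set of beneficiaries in the data changed. If those added in 2013 had claims starting shortly before, their look-back would sit near the 365-day floor, while a 2012 entrant observed since 2008 would have about four years. Returning users, or patients with an older dementia code, could then enter as new.

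The size of the step also differs by arm. The comparator share of entrants drifts down to 28.5% in 2012, turns up to 31.4% in 2013, then falls again. Undetected former users of the comparator drugs could produce that pattern. Patients indexed in 2013-2015 are 181,322 of the 444,030 matched (40.8%), so a real defect there would reach a large part of the primary comparison. No subgroup named in section 9 is by index period or look-back length.

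**Working it through.** **1. Are the counts sound?** The inputs are the index-year rows of section 8. The twelve rows sum to 583,870 and 233,467 crude, and to 222,015 in each matched arm. All four totals equal the stated N, so a misprint is unlikely.

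**2. How large are the steps?** Ratio = entrants in the year / entrants in the year before. Share = comparator / both arms. Standardized difference = (p1 - p2) / sqrt{[p1(1 - p1) + p2(1 - p2)] / 2}. As a check on the formula, crude 2008 gives -0.098, and the table prints -0.10.

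| Year | Exposed | Comparator | Both | Ratio | Comparator share | Matched std. diff. |
|---|---|---|---|---|---|---|
| 2008 | 41,242 | 22,822 | 64,064 | – | 35.6% | 0.0037 |
| 2009 | 41,633 | 23,317 | 64,950 | 1.014 | 35.9% | 0.0044 |
| 2010 | 33,970 | 14,179 | 48,149 | 0.741 | 29.4% | 0.0018 |
| 2011 | 31,276 | 12,573 | 43,849 | 0.911 | 28.7% | 0.0016 |
| 2012 | 29,262 | 11,653 | 40,915 | 0.933 | 28.5% | -0.0002 |
| 2013 | 79,415 | 36,290 | 115,705 | 2.828 | 31.4% | -0.0012 |
| 2014 | 77,490 | 32,016 | 109,506 | 0.946 | 29.2% | -0.0032 |
| 2015 | 71,638 | 27,434 | 99,072 | 0.905 | 27.7% | -0.0032 |
| 2016 | 48,353 | 15,916 | 64,269 | 0.649 | 24.8% | -0.0012 |
| 2017 | 42,820 | 12,385 | 55,205 | 0.859 | 22.4% | -0.0017 |
| 2018 | 44,058 | 12,714 | 56,772 | 1.028 | 22.4% | -0.0009 |
| 2019 | 42,713 | 12,168 | 54,881 | 0.967 | 22.2% | 0.0015 |

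By arm (exposed, comparator), the ratios are 2.714 and 3.114 in 2013, 0.675 and 0.580 in 2016, and 0.816 and 0.608 in 2010. The steps are real, and the readable text does not explain them.

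**3. Is the one-year baseline at risk?** With a 365-day minimum, claims starting on 1 January 2008 would allow almost no 2008 index dates, yet 64,064 patients are indexed that year. So 2008-2019 has to be the index window, with earlier claims in use. Their start date is simply not written down.

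**4. What does matching on year remove?** By period, the matched shares (exposed, comparator) are 35.9% and 35.6% for 2008-2012, 40.7% and 41.0% for 2013-2015, and 23.4% and 23.4% for 2016-2019. A look-back difference between arms that arises only because the arms entered in different years is therefore largely gone. What could remain is a difference between arms within the same year. The documents give no look-back lengths, so they neither show nor exclude one.

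**5. Can the number at risk be scaled from the flowchart?** Prior use removed 1,096,162 + 1,644,383 = 2,740,545 of 3,705,346 patients (74.0%), leaving 964,801. It is tempting to apply a miss rate to that total, but it would be the wrong base. The suspected mechanism concerns only patients added around 2013. Anyone with a fill in the year before index is caught however short the earlier history, so only users with a gap of more than a year can slip through.

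A later flowchart line for the study drugs removes a further 27,923 of 862,385 (3.2%). If that line is the extended look-back, which its label does not say, the older history removed few patients.

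**The case for a change.** The strongest case is that balancing index year equalizes how many patients come from each year, not the share of undetected former users in each arm within a year. Look-back length is not a listed covariate, so neither the PS nor the balance table speaks to it. The comparator share turns up in exactly the year the cohort nearly triples and then declines, as returning users passing as new would produce. CPRD is a different database and cannot test a feature of the Medicare data. A look-back table and a run by period would need no new data.

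Much of this is fair. The within-year gap is logically open, and no analysis in the readable text addresses it. That last statement has a limit: the section 4 diagrams are not shown, and the text does not say what sets analysis 3 apart.

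The decline after 2013 does not settle the matter. Pooled entrants fall 14.4% from 2013 to 2015 (115,705 to 99,072), close to the 15.0% from 2010 to 2012 (48,149 to 40,915), which fits a larger sample as well as a look-back defect. By arm, the comparator falls faster in the later period (36,290 to 27,434, or 24.4%, against 14,179 to 11,653, or 17.8%), while the exposed arm falls more slowly (9.8% against 13.9%). A different case mix in the added patients would explain that equally well.

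The argument that section 7 requires separate models for each block of years does not stand. Its reference to data sources reads naturally as Medicare and the CPRD analysis of section 9.

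**Conclusion.** No change to the plan follows. The steps are established: 2.83-fold up in 2013, 35% down in 2016 and 26% down in 2010. The path from them to a biased hazard ratio needs four further links: shorter look-back in added patients, former users missed because of it, unequal misses between arms within a year, and an effect on dementia risk large enough to matter. The documents support none of these, the miss rate may be near zero, and neither the direction nor the size of any effect can be derived.

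No stated rule or figure is shown to give a wrong result. All-available look-back with a one-year floor is a declared and defensible choice, and the part of the problem that runs through entry year is handled by the PS.

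What remains is thin description of the source: the first claims date and the reason for the steps. The analysts know these and can report them with the results, along with look-back by year and arm. Runs by index period, or with a longer minimum look-back, are optional sensitivity analyses. Each period would need its own PS fit and match (158,712, 181,322 and 103,996 matched patients in the present cohort), and the primary analysis would not change.

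This conclusion assumes that look-back does not differ materially between arms within index year. If the look-back lengths showed such a difference, an analysis by period would then be warranted.
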